13 METHODS TO PROMOTE ADHERENCE

13.1 Adherence to Study Procedures

Protocol training and adherence will be a major focus of the Investigator training. Based on our experience in prior studies, identifying and correcting non-adherence is best accomplished in a stepped approach. The CC will contact each site to offer per-participant feedback on adherence; will review episodes of non-adherence and reemphasize the importance of adherence; and will provide adherence reports to the Executive Committee.

14 PARTICIPANT SAFETY AND ADVERSE EVENTS

14.1 Institutional Review Boards

All HFN sites will submit the study protocol, informed consent form, and other study documents to their IRB for approval—the approval letter for each clinical center will be stored at the CC. Any amendments to the protocol, other than minor administrative changes, must be approved by each IRB before they are implemented.

14.2 Definitions

14.2.1 Adverse Events

An adverse event (AE) is any untoward medical occurrence associated with the use of a drug in a subject, whether or not considered drug or biologic related. An AE can therefore be any undesirable sign, symptom or medical condition occurring after starting study drug, even if the event is not considered to be related to the pharmaceutical product. Study drug includes the drug under evaluation, and any reference or placebo drug given during any phase of the trial.

Pre-existing medical conditions/diseases that were present prior to starting study treatment are only considered adverse events if they worsen after initiating study therapy(any procedures specified in the protocol).

14.2.2 Suspected Adverse Reaction

A suspected adverse reaction (SAR) is any adverse event for which there is a reasonable possibility that the drug caused the event. "Reasonable possibility" suggests there is a causal relationship between the drug and the adverse event. "Suspected adverse reaction" implies a lesser degree of certainty about causality than adverse reaction, which means any adverse event caused by a drug.

14.2.3 Serious Adverse Events

An AE or SAR is considered serious if the Investigator or sponsor believes any of the following outcomes may occur:

- Death
- Life-threatening AE: Places the subject at immediate risk of death at the time of the event as it occurred. It does not include an AE that, had it occurred in a more severe form, might have caused death.
- Persistent or significant incapacity or substantial disruption of the ability to conduct normal life functions.
- Inpatient hospitalization or prolongation of hospitalization.
- Congenital anomaly or birth defect.
- Important medical events that may not result in death, be life threatening, or require hospitalization may be considered a serious adverse event when, based upon

appropriate medical judgment, they may jeopardize the subject and may require medical or surgical intervention to prevent one of the outcomes listed in this definition above.

This determination is based on the opinion of either the investigator or sponsor (e.g., if either believes it is serious, it must be considered serious).

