14.3.1 Recording and Reporting of AEs/SAEs

Information about all adverse events, whether volunteered by the subject, discovered by investigator questioning, or detected through physical examination, laboratory test or other means, will be collected and recorded on the Adverse Event eCRF

For this study, all AES/SAEs occurring from signed informed consent to week-16 study visit will be captured on the AE/SAE eCRF. Unless exempted as described above, all AEs/SAEs, whether or not deemed drug-related or expected, must be reported by the investigator or qualified designee within 1 business day of first becoming aware of the event. The investigator/qualified designee will enter the required information regarding the AE/SAE into the appropriate module of the InForm eCRF, which will automatically result in distribution of the information to Duke Clinical Research Institute Safety Surveillance (DCRI SS). If InForm is temporarily unavailable, the event, including the investigator-determined causality to study drug, should be reported via a paper back-up SAE form to DCRI SS. Upon return of the availability of EDC system, the AE/SAE information must be entered into the eCRF.

Follow-up

When additional relevant information becomes available, the Investigator will record follow-up information according to the same process used for reporting the initial event as described above. The Investigator will follow all reportable events until resolution, stabilization or the event is otherwise explained.

Investigators are also responsible for promptly reporting AE/SAEs to their reviewing IRB/EC in accordance with local requirements.

DCRI Safety Surveillance will follow all SAEs until resolution, stabilization, until otherwise explained or until the last subject completes the final follow-up, whichever occurs first. DCRI Safety Surveillance will report all SAEs to the Heart Failure Network trial team within 1-2 business day(s) of receipt and notify the Data Safety Monitoring Board (DSMB) chair monthly.

The DSMB will review detailed safety data approximately every 6 months throughout the study.

Suspected Unexpected Serious Adverse Reaction

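### Section 14.2.3 makes an event serious on a belief that a listed outcome may follow, not on what the event led to, so SAE lists and notices can include events with no serious outcome

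*Protocol*

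**What the plan says.** Protocol Section 14.2.3 defines seriousness by an opening line, a list and a closing sentence.

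- The opening line reads: "An AE or SAR is considered serious if the Investigator or sponsor believes any of the following outcomes may occur". The list then includes death, life-threatening events, incapacity, hospitalization and congenital anomaly.
- The life-threatening item is tied to actual risk: "Places the subject at immediate risk of death at the time of the event as it occurred". It adds: "It does not include an AE that, had it occurred in a more severe form, might have caused death".
- The last item is a separate category: "Important medical events that may not result in death, be life threatening, or require hospitalization may be considered a serious adverse event". It applies when, on medical judgment, "they may jeopardize the subject and may require medical or surgical intervention to prevent one of the outcomes listed in this definition above".
- The closing sentence lets one opinion decide: "if either believes it is serious, it must be considered serious".

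Section 14.3.1 puts the classification to use: "DCRI Safety Surveillance will report all SAEs to the Heart Failure Network trial team within 1-2 business day(s) of receipt". The DSMB chair is notified monthly, and the coordinating center's safety group follows SAEs to resolution or another defined end. Under the same section, seriousness is one of three conditions for expedited reporting, with relatedness and unexpectedness.

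**The concern.** A seriousness rule normally asks what an event led to and keeps one bounded category for events that could have led there. Here the opening line applies the forward-looking test to the whole list. Taken at its word, an adverse event treated at home with full recovery is serious if someone believed at the time that admission might follow.

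At stake is the meaning of the SAE list. The trial team and the DSMB chair would read it as a list of events with serious consequences, while some entries would record only a belief about what could happen. With about 20 centers making that forecast, the same episode can be an SAE at one and a non-serious event at another.

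**Working it through.** No arithmetic applies: the question is how the parts of one definition fit together and where the classification is used.

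1. **Opening line against the death and hospitalization items.** Combined literally, an event is serious if death or admission is believed possible. Neither has to happen.

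2. **Opening line against the life-threatening item.** This item requires immediate risk of death in the event as it happened. An event thought possibly fatal later, without immediate risk, fails it but passes through the death item under the opening line. The limit stays in the text but can be bypassed.

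3. **Opening line against the important-medical-event item.** This item describes events that may not result in death, be life-threatening or require hospitalization, which presupposes that the items before it cover events that do. It then admits potential harm under stated conditions: medical judgment, jeopardy to the subject, and possible need for intervention to prevent a listed outcome. If belief in a possible outcome already suffices, most such events have qualified before these conditions are reached. The item keeps a small role where intervention is expected to prevent the outcome.

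4. **Closing sentence.** Either party's belief makes an event serious. This can only add events: under the rule as written, a central reviewer who disagrees cannot reverse a site's classification.

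5. **Where the classification matters.** Seriousness governs onward reporting to the trial team, the monthly DSMB chair notice, central follow-up and one condition for expedited reporting (Section 14.3.1). It is also one trigger for the rule on naming laboratory abnormalities (Section 14.2.4).

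6. **Where it does not matter.**
   - Site reporting is the same either way: unless exempt, "all AEs/SAEs, whether or not deemed drug-related or expected, must be reported by the investigator or qualified designee within 1 business day".
   - Sections 15.4 and 17.1 compare the occurrence of adverse events and laboratory changes. Moving an event from non-serious to serious leaves that comparison unchanged.
   - The listed disease-related events in Section 14.3 are kept out of AE and SAE capture whatever the opening line says.
   - Peak VO₂ and the sample size do not depend on it.

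**The case against.** The strongest reply is that this is loose drafting with little practical effect. Site reporting is identical for serious and non-serious events. Expedited reporting also needs relatedness and unexpectedness, and rests on the opinions of the investigator and the safety medical monitor. Many events likely to prompt thoughts of admission in this population are exempt under Section 14.3. The error is over-inclusive, so it hides nothing. These points stand, and they limit the exposure to the SAE list, the notices drawn from it and the seriousness step of expedited reporting. They do not make the opening line agree with its own list.

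A second reply is that judgment would differ between sites even after correction, because the important-medical-event item and the either-party sentence remain. That also stands. The correction confines the judgment to an item with stated conditions; it does not remove it.

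A reader might also infer three stronger points that the protocol does not support.

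- *That the opening line contradicts the life-threatening item.* The item excludes a counterfactual, a more severe form of the event. The opening line concerns the possible course of the event that happened. Both can be applied together, so the item is undercut, not contradicted.
- *That a between-arm SAE comparison would be distorted.* None is specified.
- *That the extra SAEs would fall mainly on the iron arm.* Section 18.3.4 names gastrointestinal effects as the most common with oral iron, so a larger pool of such events on iron is conceivable. But no rates by arm are given, Section 8.2 calls these preparations well tolerated with usually transient effects, and seriousness is judged under blinding.

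**Conclusion.** The point holds as a defect in a stated rule. Followed literally, Section 14.2.3 classes events as serious on a forecast, weakens two of its own items and gives no means of removing an over-classified event. The consequence is SAE listings, trial-team reports and DSMB chair notices that can include events with no serious outcome, and a seriousness criterion for expedited reporting that is met too easily.

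The size cannot be computed. Any count of extra SAEs would multiply an assumed adverse event rate by an assumed share judged able to lead to a listed outcome, and the protocol gives neither. The conclusion rests on investigators applying the opening line as written; if they already read it as asking what the event led to, little changes in practice. This is a modest point about safety reporting that does not threaten the trial's efficacy result.

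**What to change.** Reword the opening line of Section 14.2.3 along these lines: *An AE or SAR is considered serious if, in the view of either the investigator or sponsor, it results in any of the following outcomes, or if it is an important medical event as described in the last bullet.* Keep the list and the either-party sentence. The second clause is needed because an event cannot sensibly be said to result in an important medical event; without it, one mismatch would replace another.

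The cost is one sentence, plus any site instructions that repeat it. If the protocol is already approved, Sections 14.1 and 18.2 require IRB approval for changes that are not administrative, so it is best bundled with another amendment. The SAE list becomes somewhat narrower, but potentially dangerous events stay covered by the important-medical-event item, and non-exempt events are still reported by sites within the same 1 business day.

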14.2.4 Laboratory Test Abnormalities

For laboratory test abnormalities that meet the definition of a serious adverse event (SAE), which required the subject to have the investigational product discontinued or interrupted, or required the subject to received specific corrective therapy, the clinical diagnosis rather than the laboratory term will be used by the reporting investigator (e.g., anemia versus low hemoglobin value).

14.2.5 Assessment of Adverse Event Severity

The determination of adverse event severity rests on medical judgment of a medically-qualified investigator. The severity of AEs will be graded using the following definitions: **Mild:** awareness of sign, symptom, or event, but easily tolerated.

Moderate: discomfort enough to cause interference with usual activity and may warrant intervention.

Severe: incapacitating with inability to do usual activities or significantly affects clinical status, and warrants intervention.

14.2.6 Assessment of Causal Relationship

A medically-qualified investigator must assess the relationship of any AE to the use of study drug, based on available information, using the following guidelines:

- **Not related:** There is not a reasonable causal relationship to the investigational product and the adverse event.
- **Unlikely related:** No temporal association or the cause of the event has been identified, or the drug or biologic cannot be implicated.
- **Possibly related:** There is reasonable evidence to suggest a causal relationship between the drug and adverse event.
- **Related:** There is evidence to suggest a causal relationship, and the influence of other factors is unlikely.

The Investigator reports causality, but the sponsor retains the final decision on causality when filing to the FDA.

14.2.7 Expectedness

The expectedness of an AE or SAR shall be determined according to the specified reference document containing safety information (e.g., most current investigator's brochure or product

label). Any AE that is not identified in nature, severity, or specificity in the current study drug reference document(s) (e.g., investigator's brochure) is considered unexpected. Events that are mentioned in the product label as occurring with a class of drugs or as anticipated from the pharmacological properties of the drug, but not specifically mentioned as occurring with the particular drug under investigation are considered unexpected.

14.3 Anticipated Adverse Events and Procedure Effects

The following AEs are anticipated, disease-related events in patients with HF with reduced EF (HFrEF):

- Arrhythmias
- Sudden cardiac death
- Acute coronary syndrome
- Unplanned hospitalization, ER visit or clinic visit for worsening HF
- Cerebrovascular event
- Venous thromboembolism
- Lightheadedness, presyncope or syncope
- Worsening renal function

All anticipated disease related events, will not be captured as AEs/SAEs during the study, but will be entered on the appropriate eCRF module.

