AEs that meet the criteria of serious, related to study drug, and unexpected per investigator brochure or product labeling, qualify for expedited reporting to the regulatory authorities. DCRI will notify the FDA and all participating investigators in a written IND safety report of an SAR that is serious and is unexpected, based on the opinion of the investigator and DCRI safety medical monitor, as soon as possible, but not later than 15 calendar days after the event is confirmed to be a serious, unexpected SAR and qualifies for expedited reporting. DCRI will identify all safety reports previously filed with the IND concerning a similar SAR, and will analyze the significance of the SAR in light of the previous, similar reports. Follow-up reports will be sent to investigators to inform and update them about an important suspected adverse reaction if it significantly affects the care of the subjects or conduct of the study.

The site investigator will be responsible for reporting adverse events and unanticipated problems involving risks to subjects to their local IRBs/IECs in accordance with local regulations.

Day Zero

Day zero (0) is the calendar day that DCRI is first notified of an event. Day zero can also be the date the event qualified for expedited reporting as determined by the DCRI Safety Medical Monitor.

Pregnancy

Pregnancy occurring during a clinical investigation, although not considered a serious adverse event, must be reported to DCRI within the same timelines as a serious adverse event. The pregnancy will be recorded on the appropriate paper pregnancy tracking form. The pregnancy will be followed until final outcome. Any associated AEs or SAEs that occur to the mother or fetus/child will be recorded in the AE/SAE eCRF, within InForm.

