15.4 Analysis of Safety Data and Statistical Monitoring Plan

Interim data analysis for efficacy and futility will not be conducted due to relatively small size and short duration of this clinical trial. Safety data, summarized at the treatment level, will be assessed approximately every 6 months by the NHLBI-appointed DSMB. The safety analyses will be based on the entire ITT population. Safety will be evaluated by comparing the occurrence of AEs and changes in laboratory values of the active arm compared to placebo. The number and percentage of participants experiencing AEs will be tabulated by treatment group, body system, and preferred term. The percentages between treatment groups will be compared using Fisher's exact test.

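### Eight disease-related event types are exempt from AE/SAE capture with no exception for suspected drug relation, and five of them have no stated between-arm comparison

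*Protocol*

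**What the plan says.** Section 14.3 lists eight anticipated event types: arrhythmias; sudden cardiac death; acute coronary syndrome; unplanned hospitalization, emergency or clinic visit for worsening heart failure; cerebrovascular event; venous thromboembolism; lightheadedness, presyncope or syncope; and worsening renal function. It then states: "All anticipated disease related events, will not be captured as AEs/SAEs during the study, but will be entered on the appropriate eCRF module".

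Section 14.3.1 says two things about recording. Its first paragraph covers "Information about all adverse events, whether volunteered by the subject, discovered by investigator questioning, or detected through physical examination, laboratory test or other means" and sends all of it to the AE form. The next paragraph honours the exemption: "Unless exempted as described above, all AEs/SAEs, whether or not deemed drug-related or expected, must be reported by the investigator or qualified designee".

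Three later steps are worded in terms of AEs or SAEs:

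- Causality, Section 14.2.6: "A medically-qualified investigator must assess the relationship of any AE to the use of study drug".
- Notice to the trial team and, monthly, to the DSMB chair, Section 14.3.1: SAEs.
- Expedited reporting, Section 14.3.1: "AEs that meet the criteria of serious, related to study drug, and unexpected per investigator brochure or product labeling, qualify for expedited reporting".

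On analysis, Section 15.4 states "Safety will be evaluated by comparing the occurrence of AEs and changes in laboratory values of the active arm compared to placebo", and Section 17.1 repeats the sentence for the DSMB. Section 15.4 adds "The number and percentage of participants experiencing AEs will be tabulated by treatment group, body system, and preferred term", with Fisher's exact test between arms.

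**The concern.** Exempting anticipated disease events from routine AE/SAE reporting is not in itself a fault. It needs two safeguards: a way back into the SAE route when the drug is suspected, and a by-arm tabulation of the exempt events, so that an excess on active treatment is visible even when no single case looks drug-related. The protocol states neither.

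The exempt list holds the events through which cardiovascular harm would appear, and some of those through which renal harm would. If sites and statisticians follow the text as written, the DSMB's stated comparison and the final AE tables omit them. Sites also have two incompatible instructions about which form to use, so the AE table could depend on which paragraph a site followed.

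**Working it through.** The protocol gives no figure for these events, so there is none to reproduce. The check compares its sections.

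**Step 1: is the exemption conditional?** The list in 14.3 is by event type. Nothing in it refers to seriousness or suspected relation to study drug. In 14.3.1, the clause about events being reportable whether or not they are thought drug-related follows the opening exception for exempt events, so it does not bring listed events back.

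**Step 2: do the recording rules agree?** No. Under 14.3 a listed event is not captured as an AE or SAE. Under the first paragraph of 14.3.1, information on all adverse events goes on the AE form. A listed event meets the AE definition in 14.2.1 if it arises, or worsens, after study drug is started.

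**Step 3: what follows for a listed event that may be drug-related?** Causality assessment, SAE notice and expedited reporting all start from an AE or SAE. An event never captured as one enters none of them on a literal reading. Section 14.2.7 judges expectedness against the drug's reference document, and the side effects in Sections 8.2 and 18.3.4 are gastrointestinal. Subject to the product label, which is not shown, a drug-related stroke or arrhythmia could therefore qualify as serious and unexpected and yet be exempt.

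**Step 4: which listed types have a stated by-arm comparison?**

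| Listed type | Comparison stated in the protocol |
|---|---|
| Arrhythmias | None |
| Acute coronary syndrome | None |
| Cerebrovascular event | None |
| Venous thromboembolism | None |
| Lightheadedness, presyncope, syncope | None |
| Sudden cardiac death | Within the exploratory time-to-event composite (15.3) |
| Worsening HF | Hospitalizations only, in the same composite; emergency and clinic visits are not part of it |
| Worsening renal function | Partly: laboratory changes (15.4, 17.1) and exploratory creatinine/cystatin C (4.3) |

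That is 5 of 8 with none and 3 of 8 with partial coverage. Section 15.4 rules out interim efficacy analysis, and nothing places the exploratory composite before the DSMB. After randomization, scheduled blood is drawn only at week 16 (Section 11.3, Appendix A), so a renal event that had resolved by then would not show.

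**Step 5: scale, by assumption.** The only input from the protocol is the planned 220 participants (Section 15.5). The assumed share with at least one listed event is 5% to 15%.

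- 0.05 × 220 = 11 participants; 0.15 × 220 = 33 participants.
- With an assumed 110 per arm, a split of 5 against 15 (20 in all, 20/220 = 9.1%) gives a two-sided Fisher p = 0.033.
- A split of 10 against 22 (32 in all, 32/220 = 14.5%) gives p = 0.034.

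Imbalances of this size would be absent from the AE table and its Fisher test. Any part due to death or HF hospitalization could still show in the exploratory analysis.

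**The case against.** The strongest reply is that the protocol nowhere confines the DSMB to the AE form. Sections 15.4 and 17.1 speak of safety data summarized by treatment, and 14.3.1 promises the board detailed safety data about every six months. The lead-in to the list calls the events AEs, so a comparison of AEs could be read to include them, and 14.3 governs where they are recorded, not whether they are analysed. Table content can also be settled in the SAP or a DSMB charter.

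Much of this stands. A reader might infer that the DSMB cannot see these events, that they are lost, or that all eight lie outside any comparison. The documents support none of these:

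- The events go to other eCRF modules, and Section 16.1 provides event forms for death and hospitalization.
- Sudden cardiac death and HF hospitalization have a planned comparison, and renal function has laboratory data. Core-laboratory blood is drawn at baseline as well as at week 16.
- Only sudden cardiac death is listed. Deaths not falling under a listed event remain SAEs.
- The protocol gives no rates, so nothing shows what share of serious events is exempt.

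A reader might also infer that expedited reporting is definitely blocked. That goes too far: an event judged drug-related is arguably not disease-related and so not exempt, and 14.3.1 separately requires sites to report unanticipated problems involving risks to their IRBs.

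Two points remain. Where the protocol does say what is compared, it names AEs and laboratory changes and does not add the exempt events. And an SAP can add tables but cannot change what investigators record, assess for causality or report; those rules are in the protocol, and they conflict.

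**Conclusion.** The concern holds in this form: the exemption has no exception for suspected drug relation, it contradicts the recording rule in 14.3.1, and the stated safety comparison does not add the exempt events. Five of the eight types have no stated comparison by arm; the other three have partial coverage, mainly exploratory or from blood drawn at week 16.

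The text is silent on by-arm tabulation of the disease-event module; it does not forbid it. The count of 11 to 33 participants rests wholly on the assumed 5% to 15% and only illustrates scale. The primary endpoint is unaffected and the data exist. This should be fixed, but it does not undermine the trial's main analysis.

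**What to change.** 1. In Sections 15.4 and 17.1, state that every DSMB report and the final safety analysis tabulate by arm, alongside AEs and SAEs, all deaths, all hospitalizations and every event from the disease-event module, including emergency and clinic visits for worsening HF.
2. Reconcile Section 14.3 with 14.2.6 and 14.3.1 so that they agree on where a listed event is recorded. State that a listed event judged possibly related or related to study drug is not exempt and enters the AE/SAE and expedited-reporting route. Listed events judged not related or unlikely related can stay on the module. This requires the relatedness assessment of 14.2.6 to be made for listed events too.

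The cost is protocol wording, a relatedness item on the module if it lacks one, a few extra tables from data already collected, and a few more SAE forms. Sample size and the efficacy analyses do not change.
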